signal of the intestinal wall, resulting in falsely high MSOT signals in the determination of inflammatory activity. Therefore, in this study, influences of a standardized dietary¹⁰ on the MSOT signal of the intestinal wall will be investigated in a longitudinal design and optoacoustic signals will be compared between subjects in fasting and postprandial states. Because the postprandial increase in intestinal blood flow is predominantly a result of the local presence of chyme in the intestine,¹¹ a simultaneous determination of intestinal transit of chyme during MSOT measurement would be helpful to validate whether postprandial changes in MSOT signals are attributable to hyperemia in the corresponding bowel segment. With MSOT, in addition to the determination of hemoglobin, the detection of exogenous chromophores is also possible. Therefore, in this study, oral administration of the nonabsorbable dye ICG will be used for noninvasive identification of the chyme.¹² We believe that the combination of exogenous and endogenous chromophores thus allows accurate co-localization and registration of intestinal wall blood flow patterns and chyme transit. This information enables accurate anatomical mapping of interfering influences on the determination of hemoglobin using MSOT.

The time course of postprandial hyperemia in the different sections of the gastrointestinal tract has been scientifically investigated in many studies. While an increase in blood flow in the stomach and duodenum can be detected after 30-60 minutes, it takes much longer for postprandial hyperemia to be detected in the areas used to measure inflammatory activity with MSOT in IBD such as the terminal ileum and sigmoid colon. An increase in blood flow in the ileum can be measured after 120 minutes at the earliest,¹ and the arrival of chyme in the colon and the accompanying local increase in blood flow occur after approximately 240-300 minutes.^{13,14} Therefore in this study postprandial changes in the MSOT hemoglobin signal will be investigated over period of 7 hours.

Bibliography

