- The quantitative amount of oxygenated/deoxygenated hemoglobin in the intestinal wall determined by MSOT differs between fasting persons and persons after ingestion food.
- The quantitative amount of oxygenated/deoxygenated hemoglobin in the intestinal wall determined by MSOT changes after the ingestion of food.
- The postprandial changes in the quantitative amount of oxygenated/deoxygenated hemoglobin in the intestinal wall determined by MSOT occur successively in subsequent sections of the gastrointestinal tract, from oral to aboral.
- A relationship exists between postprandial changes in the quantitative amount of oxygenated/deoxygenated hemoglobin in the wall of the gastrointestinal tract determined by MSOT and postprandial changes in Doppler sonographic signals in the major splanchnic arteries (truncus coeliacus, superior mesenteric artery, inferior mesenteric artery).
- The postprandial changes in the quantitative amount of oxygenated/deoxygenated hemoglobin in the intestinal wall determined by MSOT are associated with the presence of chyme in the lumen of the gastrointestinal tract.
- Measurement of ICG signals within the lumen of the gastrointestinal tract using MSOT after ingestion of ICG-containing food indicates the presence of chyme within the lumen of the gastrointestinal tract.
- A relationship exists between postprandial changes in the quantitative amount of oxygenated/deoxygenated hemoglobin in the wall of the gastrointestinal tract determined by MSOT and postprandial changes in the ICG signal determined by MSOT within the lumen of the gastrointestinal tract after ingestion of ICG-containing food.

Primary objectives:

- Comparison of oxygenated/deoxygenated hemoglobin signal in the wall of the gastrointestinal tract measured by MSOT between fasting subjects and subjects after ingestion of food.

Secondary objectives:

- Measurement of the postprandial change in the oxygenated/deoxygenated hemoglobin signal in the wall of the gastrointestinal tract measured by MSOT over time and over the different sections of the gastrointestinal tract.
- Comparison of the Doppler sonographic signal in the large arteries of the splanchnic area between fasting subjects and subjects after ingestion of food.
- Measurement of the postprandial change in the Doppler sonographic signal in the large splanchnic arteries over time and over the different splanchnic arteries.

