The study starts for the participants at 10 pm on the day before the first examination day with adherence to the fasting period. On the first examination day, the preprandial measurement is performed at 8 am after 10 hours of fasting in all study arms. The preprandial measurement starts with the sonographic localisation of the sections of the gastrointestinal tract that will be examined in the following measurements with MSOT and Doppler sonography. Skin markings are made with a skin-compatible marker pen for better reproducibility of the following measurements. The further procedure of the preprandial measurement and each of the following postprandial measurements will follow an identical measurement protocol. A period of 20 minutes is planned for each measurement protocol. Depending on the study arm, the subjects remain fasting throughout all the measurements of the day (study arm A) or receive a standardised breakfast with or without ICG supplement (study arm B/C) 30 minutes after the start of the preprandial measurement. After the subjects have eaten the breakfast within 15 minutes, the first postprandial measurement takes place exactly 60 minutes after the preprandial measurement in all study arms. In the following 6 hours, further postprandial measurements are taken at 60-minute intervals, so that the last measurement takes place exactly 7 hours after the start of the preprandial measurement. 4 hours after breakfast, the subjects from study arms B and C receive another standardised meal to simulate regular food intake. This meal does not contain ICG. The subjects in study arm A remain fasting throughout all the measurements of the day.

On each measurement day two subjects are examined in parallel with a time offset of 30 minutes. This means that the entire examination for the second participant begins at 8:30 am.

[figure not shown]

Figure 1: Course of one examination day for one participant. X-axis is time in minutes with 0 being the beginning of the preprandial measurement at 8:00 or 8:30 am..

In a crossover design, each participant is examined on three measurement days according to the three study arms. There must be a minimum time interval of 48 hours between each examination day for the participant. The order of the examination days is predetermined:

1st examination day (study arm A): Fasting

2nd examination day (study arm B): Standardised breakfast

3rd examination day (study arm C): Standardised breakfast with ICG

[figure not shown]

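### The evening meal before each study day is not standardised, so residue in the colon cannot be excluded during the scans and may differ between the days compared

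*Combined protocol and SAP*

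**What the plan says.** Section 9, Time schedule, starts the fast the evening before: "The study starts for the participants at 10 pm on the day before the first examination day with adherence to the fasting period". That sentence names only the first day, but the next extends the fast to every arm: "the preprandial measurement is performed at 8 am after 10 hours of fasting in all study arms". Two participants are examined per day, and "the entire examination for the second participant begins at 8:30 am". Scans are hourly, and "the last measurement takes place exactly 7 hours after the start of the preprandial measurement". In arms B and C breakfast comes "30 minutes after the start of the preprandial measurement", and a second meal follows: "4 hours after breakfast, the subjects from study arms B and C receive another standardised meal to simulate regular food intake".

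Section 9 also fixes the composition of breakfast and second meal by sex and body weight, and has each subject drink 150 ml of water before every measurement so that the stomach is evenly filled. The text available has no comparable rule for the evening meal.

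Section 4 attributes postprandial hyperaemia mainly to chyme being locally present, and says that "the arrival of chyme in the colon and the accompanying local increase in blood flow occur after approximately 240-300 minutes". The fifth hypothesis in Section 5 is that postprandial haemoglobin changes "are associated with the presence of chyme in the lumen of the gastrointestinal tract". Section 6 lists four MSOT sites, two of them colonic. Section 7 fixes the order A (fasting), B (breakfast), C (breakfast with ICG), with at least 48 hours between days and no randomisation or blinding.

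**The concern.** The plan takes care to control what is in the lumen on the study day but leaves the preceding meal open. If food in a bowel segment raises wall haemoglobin, as the plan assumes, an overnight fast may not give the colon the same starting condition as the stomach: on the plan's arrival time, the evening meal passes into the colon during the fast.

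Three things are at stake:

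- **Precision.** The fasting-fed comparison is made within a person across separate days. Evening meals that differ between those days add avoidable variation at the colonic sites, in a study of only 10 people.
- **Possible bias.** Because the order is the same for everyone, a systematic diet difference between days cannot be separated from arm. For example, someone facing the all-day fast might eat more or later the evening before. The documents do not show that this happens, but under the plan's mechanism it could raise the fasting colonic signal and shrink the primary contrast.
- **Interpretation.** ICG labels only the arm C breakfast. A colon without ICG signal is one that the labelled breakfast has not visibly reached, and should not be read as a colon without chyme.

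**Working it through.** **Inputs.** Fast from 22:00; first scan 08:00 (08:30 for the second participant); last scan 7 h later; breakfast 30 min after the start and eaten within 15 min; second meal 4 h after breakfast (all Section 9). Colon arrival 240-300 min after intake (Section 4). Evening meal time is not given; I assume 18:00 to 22:00.

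**The plan's own figures.** 22:00 to 08:00 is 10 h, as stated. The second participant has 10.5 h if also fasting from 22:00. Seven hourly intervals give 7 × 60 = 420 min, so the last scan is at 15:00 (or 15:30).

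**Evening meal.** Colon entry = meal time + 240 to 300 min. Time since entry = scan time − entry time.

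| Evening meal | Enters colon | Hours before 08:00 scan | Hours before 15:00 scan |
|---|---|---|---|
| 18:00 | 22:00-23:00 | 9-10 | 16-17 |
| 20:00 | 00:00-01:00 | 7-8 | 14-15 |
| 22:00 | 02:00-03:00 | 5-6 | 12-13 |

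Add 0.5 h for the second participant. The meal has entered the colon before scanning in every row. It is still there at the first scan only if colonic residence exceeds about 5-10 h, and at the last only if it exceeds about 12-17 h. The plan gives no residence time and does not break arrival down by colonic segment, so these are conditions and not findings.

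**Study meals.** Breakfast, eaten between 30 and 45 min, reaches the colon between 30 + 240 = 270 and 45 + 300 = 345 min. Of the eight scans, only those at 300, 360 and 420 min can show it there. The second meal, at 270-285 min, would arrive between 270 + 240 = 510 and 285 + 300 = 585 min, after the last scan. The fed colonic signal therefore rests on at most three scans per day, which leaves little room for avoidable noise.

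**Illustration of noise (all values assumed).** Take a paired t-test with n = 10, two-sided 5%, and a standardised within-subject difference of 1.0. If diet adds a fraction v to the variance of the difference, the effect becomes d = 1/√(1 + v), with noncentrality d√10 on 9 degrees of freedom.

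| v | d | Power |
|---|---|---|
| 0 | 1.00 | 80% |
| 0.25 | 0.89 | 71% |
| 0.50 | 0.82 | 63% |
| 1.00 | 0.71 | 51% |

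The documents give no effect size, standard deviation or power, and nothing that fixes v. The table shows only how sensitive 10 subjects are to extra day-to-day variation.

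**The case against.** The strongest reply is that a reader might infer that the evening meal demonstrably lies in the transverse and sigmoid colon during the scans and contaminates the fasting comparator. The documents do not support that. Section 4 gives arrival in the colon as a whole, with no residence time and no time to reach either scanned site. It also ties the rise in blood flow to arrival and gives no duration for it, so older residue is not shown to raise the signal at 08:00-15:00. That stands, and the point is limited to what cannot be excluded.

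Nor do the documents show that evening meals differ between days; they only allow it. The plan never claims a chyme-free fasting colon, and an ordinary overnight fast is a legitimate comparator for whether eating changes the MSOT signal. The ICG analysis in Section 5 correlates changes and does not need a strict split into chyme present and absent. These replies stand too; what remains is how colonic results without ICG signal are interpreted.

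Each day has its own preprandial scan, which could remove a stable day-specific offset. This answers only part of the point: Section 10 does not say that the baseline enters the comparison, and a baseline would not remove an effect that changes over the seven hours.

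If residence is long, meals before the evening meal matter as well, and repeating one meal is an incomplete control. That is fair, but the most recent unstandardised meal is the simplest to fix.

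Finally, the figures and the participant information attached to the protocol were not available, so a rule on the evening meal may exist there.

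**Conclusion.** The point holds as a low-cost improvement; it does not show that the plan is wrong as written. In the text available the evening meal is not standardised across the three days. On the plan's own arrival time a meal finished by 22:00 has entered the colon 5-6 h before the 08:00 scan. Residue at the two colonic sites therefore cannot be excluded in any arm and may vary between days. The residence thresholds rest on the assumed 18:00-22:00 range of meal times.

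The expected consequence is extra within-subject noise. It becomes bias only if diet changes systematically along the A-B-C order, which is possible but not shown. The plan's figures raise no comparable concern for the antrum or terminal ileum after a 10-hour fast. Neither the effect on the haemoglobin signal nor the gain from the change can be computed from the documents.

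**What to change.** Add to Section 9, Time schedule: with the fasting period unchanged, each participant eats the same self-chosen evening meal at about the same clock time before each of the three examination days. Content and time are recorded before day A and the meal is repeated before days B and C. Deviations are recorded and examined in a sensitivity analysis of the colonic sites; they do not force a new examination date, which would be out of proportion when two participants share each day.

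In the report, describe the transverse and sigmoid results as the effect of breakfast added to a colon that may hold residue, and do not treat absence of ICG signal as absence of chyme. This wording can be adopted even if data collection has begun.

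The cost is one instruction, one diary line and a small burden on participants. If the participant information already contains such a rule, it need only be carried into the protocol.

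### In both fed arms, every colonic reading in or after the expected breakfast-chyme window also follows a second meal, so timing alone cannot assign a late colonic haemoglobin rise to breakfast

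*Combined protocol and SAP*

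**What the plan says.** **Schedule (section 9, Time schedule).** Arms B and C receive breakfast "30 minutes after the start of the preprandial measurement". It is eaten within 15 minutes, and "the first postprandial measurement takes place exactly 60 minutes after the preprandial measurement in all study arms". Thereafter "further postprandial measurements are taken at 60-minute intervals, so that the last measurement takes place exactly 7 hours after the start" of the preprandial measurement. Then: "4 hours after breakfast, the subjects from study arms B and C receive another standardised meal to simulate regular food intake". That meal carries no ICG, and the measurement protocol gives it the same composition as breakfast. Arm A fasts all day.

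**Expected transit (section 4).** Gastric and duodenal hyperaemia is expected after 30-60 minutes and ileal hyperaemia after 120 minutes at the earliest. For the large bowel, "the arrival of chyme in the colon and the accompanying local increase in blood flow occur after approximately 240-300 minutes". The postprandial increase is described as "predominantly a result of the local presence of chyme in the intestine".

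**Hypothesis (section 5).** Haemoglobin changes are expected to "occur successively in subsequent sections of the gastrointestinal tract, from oral to aboral". The time course over sections is a secondary objective. The primary objective compares fasting with fed subjects. Two of the four measured segments are colonic (section 6).

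**Analysis (section 10).** The plan lists means with standard deviations, Spearman correlation, and Mann-Whitney or analysis of variance. Nothing separates readings after one meal from readings after two.

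**The concern.** The plan's transit times and its meal schedule meet at the colon. Breakfast chyme is expected there just as the subject eats again. A rise in transverse or sigmoid haemoglobin from minute 300 would naturally be read as the last step of the oral-to-aboral sequence, but it would also coincide with recent eating. The fasting arm does not resolve this, because from minute 300 the fed-fasting contrast is two meals against none.

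Section 4 names the sigmoid colon among the sites used to measure inflammatory activity and gives falsely high signals as a motive for the study. Assigning a late colonic rise to the wrong meal would give the wrong interval after eating for that risk.

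**Working it through.** **Inputs.** Minute 0 is the start of the preprandial measurement. Breakfast runs from minute 30 to minute 45 at the latest, and each measurement takes 20 minutes (section 9). Section 4 gives 30-60 minutes for the stomach, 120 at the earliest for the ileum and 240-300 for the colon. The plan does not say whether the four hours, or the transit times, run from the start or the end of breakfast, so both counts are shown.

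**The plan's own figure.** First postprandial reading at 60, then six more at 60-minute steps: 60 + 6 × 60 = 420 minutes = 7 hours. This reproduces the stated duration.

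**Second meal and colonic window.**
- From breakfast start: second meal at 30 + 240 = 270; window 30 + 240 = 270 to 30 + 300 = 330.
- From breakfast end: second meal at 45 + 240 = 285; window 285 to 45 + 300 = 345.

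| Reading starts (min) | After breakfast start | After second meal at 270 | After second meal at 285 | Against colonic window |
|---|---|---|---|---|
| 60 | 30 | – | – | before |
| 120 | 90 | – | – | before |
| 180 | 150 | – | – | before |
| 240 | 210 | – | – | before |
| 300 | 270 | 30 | 15 | inside |
| 360 | 330 | 90 | 75 | after |
| 420 | 390 | 150 | 135 | after |

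The last column is the same on both counts. The reading at 240 ends at 260, which is 10 minutes before the window opens (25 minutes on the later count). So none of the three readings in or after the window precedes the second meal.

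**Where second-meal chyme can act within the measured day.**
- Stomach: 270 + 30 = 300 to 270 + 60 = 330 (315 to 345 on the later count). Antral readings from 300 may be affected.
- Ileum: 270 + 120 = 390 at the earliest (405). The reading at 420 may be affected; those at 300 and 360 are not.
- Colon: 270 + 240 = 510 at the earliest (525). This is after the last reading, so a second-meal effect on the colon would have to be non-local.

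**An internal comparison already in the data.** Readings at 60, 120 and 180 start 30, 90 and 150 minutes after breakfast starts. Readings at 300, 360 and 420 start 30, 90 and 150 minutes after a second meal at 270. The readings at 0 and 240 each start 30 minutes before the respective meal. On the plan's figures, breakfast chyme is not yet in the colon at 60-180, so a colonic change there would indicate a response to eating itself. If the second meal starts at 285, the later lags are 15, 75 and 135 minutes and the match is 15 minutes off.

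**The case against.** The strongest case against the point is that the timing matters little. The second meal is deliberate. The plan treats hyperaemia as mainly local, and second-meal chyme cannot reach the colon before the last reading. In arm C only breakfast is labelled, so colonic ICG marks breakfast chyme. The identical breakfast also shows, in both fed arms, whether eating alone moves the colonic signal. Finally, the sequence is a secondary objective of an exploratory study in 10 subjects.

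Most of this stands, and it limits the size of the point. A reader might infer that a late colonic rise cannot be attributed at all, that the aboral end of the sequence is unanswerable, or that nothing controls for the second meal. The documents do not support these readings: arm C ICG and the matched readings after breakfast both bear on the question. Nor do sections 4 and 9 contradict each other, since a transit time and a meal time can both be correct.

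Two parts do not dispose of the point. First, locality cannot simply be assumed, because section 5 makes the association between haemoglobin change and luminal chyme a hypothesis under test. Second, ICG shows that breakfast chyme is present but does not remove the recent meal: an ICG-positive reading at 300-420 still follows it. Section 10 plans neither the matched comparison nor any use of ICG to separate the two meals.

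**Conclusion.** The point holds in a limited form. In arms B and C, all three readings in or after the expected colonic window follow the second meal, by about 30, 90 and 150 minutes (15, 75 and 135 if the four hours run from the end of breakfast). No arm has breakfast alone. A late colonic rise therefore cannot be assigned to breakfast chyme from timing alone, and arm B, without dye, is the weaker of the two fed arms on this.

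The fed-fasting comparison remains answerable as a comparison of eating with not eating. What is weakened is attribution to one meal.

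The conclusion rests on the plan's approximate transit times; in a subject with faster transit, the reading at 240 could catch arrival before the second meal. It also rests on a non-local colonic response being possible. The plan's wording leaves that open, but the documents neither describe nor quantify such a response.

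**What to change.** Add the following to section 10. Meals and schedule stay as they are.

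1. Report fed-arm readings from minute 300 as following two meals. Do not use late colonic changes in arm B on their own as evidence of breakfast-chyme arrival or of the aboral end of the sequence.
2. Compare colonic haemoglobin change from the reading just before each meal (0 and 240) at matched lags: 60/120/180 after breakfast against 300/360/420 after the second meal, within subject and against arm A at the same minutes. A rise only after the second meal argues against a pure remote response to eating. The comparison is imperfect, because breakfast follows an overnight fast and the second meal does not.
3. In arm C, show colonic haemoglobin beside ICG at each late reading, descriptively. Do not require ICG for a change to count: that would select haemoglobin changes on the variable they are to be correlated with and help build in the expected order. Do not treat ICG-negative readings as a clean estimate of the second meal's effect, since absent signal may mean slow transit or failed detection.
4. For the sequence, flag antral readings from 300 and the ileal reading at 420 as possibly affected by second-meal chyme. Keep the ileal readings at 300 and 360.

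The cost is analysis wording. The downside is that the colonic part of the sequence then rests on weaker, descriptive evidence.
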